Official title: Persistent Lymphopenia in Liver Transplantation and Its Molecular Insights for Hepatocellular Carcinoma

NCT number:

Document date: 2021/10/20

Study Protocol and Statistical Analysis Plan:

The subjects of this study were HCC patients with low lymphocytes (experimental group) and normal lymphocytes (control group). The sample type was blood and was divided into two parts: retrospective and prospective.

The source of retrospective blood (including serum, plasma or white blood cells) is to apply for specimens from tissue banks and biobank of Kaohsiung Chang Gung Memorial Hospital (KCGMH). At the same time, the patient's medical record, such as gender, age, lymph node, etc. will also be requested. The number of cells, total number of white blood cells, survival, recurrence, biochemical test data and other information are collected.

Prospective blood is newly collected. The source is that during the patient's treatment, about 20ml blood is drawn during routine examinations. This will not increase the burden on the patient. We will ask the patient one week before collecting the specimen if he is willing to provide the specimen for research purposes, and we guarantee that his personal information and privacy will not be disclosed. Unused specimens will be destroyed after the research is completed.

We will perform retrospective analysis at first. 145 HCC patients will be divided into 2 groups with or without lymphopenia, followed by comparing the effects of clinical data between them. Blood samples will be collected to analyze the impact and expression of protein, gene and microRNA (miRNA). Next Generation Sequencing (NGS) will be applied to find unknown important factors. In prospective study, 20 lymphopenia and 25 non-lymphopenia HCC recipients were enrolled, and a phenotypic analysis of peripheral blood lymphocytes was performed using multiparameter flow cytometry to identify the major immune cell subsets and validate previous results.

One-way analysis of variance will be used with Bonferroni's post hoc analysis for comparison between multiple groups. Student's t test will be used for comparison of continuous data between two groups while chi-square for discrete data. Significance is defined as $P < 0.05$.

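### The lymphopenia comparison is observational and every named test is covariate-unadjusted, so a crude difference in recurrence or survival cannot be read as independent of case mix

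*Combined protocol and SAP*

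**What the plan says.** The document is a single section, Study Protocol and Statistical Analysis Plan. Its opening paragraph defines the groups: "The subjects of this study were HCC patients with low lymphocytes (experimental group) and normal lymphocytes (control group". The labels are those of an experiment, but nothing is assigned. The analysis paragraph then says "145 HCC patients will be divided into 2 groups with or without lymphopenia, followed by comparing the effects of clinical data between them".

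For the retrospective part, the paragraph on stored blood lists the record data: "At the same time, the patient's medical record, such as gender, age, lymph node, etc. will also be requested", and "The number of cells, total number of white blood cells, survival, recurrence, biochemical test data and other information are collected". Survival and recurrence appear there as data items. No primary outcome, hypothesis or follow-up period is given.

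The final paragraph gives the whole analysis: "One-way analysis of variance will be used with Bonferroni's post hoc analysis for comparison between multiple groups" and "Student's t test will be used for comparison of continuous data between two groups while chi-square for discrete data", with significance at P < 0.05. There is no regression model, stratification, matching or covariate list.

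The molecular work is exploratory in its own words: "Next Generation Sequencing (NGS) will be applied to find unknown important factors". The flow-cytometry part is small: "In prospective study, 20 lymphopenia and 25 non-lymphopenia HCC recipients were enrolled". No covariate request is stated for that cohort.

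**The concern.** Patients with low lymphocyte counts may differ from the others in age, liver function or extent of disease, and each of these could bear on recurrence or survival. The named tests cannot separate a link with lymphopenia from such differences. Bonferroni corrects for multiple comparisons, not for case mix.

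Age, sex and biochemical data are requested and may well be compared between the groups. That could reveal an imbalance, but it would not remove it from the outcome comparison, and a non-significant baseline test is weak reassurance at this sample size.

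At stake is interpretation: a significant P value between groups called experimental and control is easily taken for more than a crude association.

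**Working it through.** **No figure to reproduce.** The plan gives 145 patients, 20 versus 25 patients, and P < 0.05. It gives no split of the 145, event rate, follow-up or power. The structural point rests on reading the named methods: none, as named, has a covariate term.

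**Illustration; every input except 145 and 0.05 is assumed.** One binary confounder has prevalence q1 in the lymphopenia group and q0 in the other. Recurrence risk is rH with it and rL without it, and lymphopenia has no effect once the confounder is known. The crude risk in a group is q × rH + (1 − q) × rL.

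- Small imbalance (40% vs 30%; recurrence 40% vs 15%): 0.4×0.40 + 0.6×0.15 = 25.0%, against 0.3×0.40 + 0.7×0.15 = 22.5%.
- Middle (50% vs 30%; recurrence 40% vs 15%): 0.5×0.40 + 0.5×0.15 = 27.5%, against 22.5%; odds ratio 1.31.
- Large (60% vs 30%; recurrence 50% vs 10%): 0.6×0.50 + 0.4×0.10 = 34.0%, against 0.3×0.50 + 0.7×0.10 = 22.0%; odds ratio 1.83.

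Chance that a two-sided chi-square test at 0.05 is significant, by exact enumeration over splits 72/73, 64/81, 48/97 and 29/116:

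| Scenario | Uncorrected | With Yates correction |
|---|---|---|
| Equal risks | 4.9-5.6% | 2.5-3.4% |
| Small | 6.4-7.5% | 3.6-4.9% |
| Middle | 9.7-12.3% | 6.1-8.6% |
| Large | 28.2-38.6% | 20.8-31.6% |

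**Would a baseline test show the imbalance?** An uncorrected chi-square on the confounder itself detects the large imbalance 85.0-95.8% of the time and the middle one 52.9-69.5%. It therefore misses them in about 4-15% and 30-47% of studies.

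**What adjustment does.** The large and middle scenarios were simulated as time to event (exponential times, fixed follow-up, 10,000 draws per case). A Cox model with lymphopenia alone was significant in 29.4-36.2% (large) and 9.5-10.7% (middle). With four terms (lymphopenia, the confounder and two unrelated covariates) this fell to 4.5-5.3%, and standard errors were 3-5% larger. These figures illustrate the remedy. The plan names no time-to-event method, so they are not error rates of the plan as written.

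**Imperfect measurement.** Stratifying on a version of the confounder with 90% sensitivity and specificity leaves 9.0-9.9% (large) or 5.8-5.9% (middle). At 80% it leaves 15.8-19.3% or 7.3-7.6%.

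**How many terms.** Expected recurrences in the large scenario are 72×0.34 + 73×0.22 = 40.5 at an even split, falling to 29×0.34 + 116×0.22 = 35.4. In the middle scenario they run from 36.2 to 34.1. At ten events per term, a rule of thumb, that allows four terms in one of these eight cases and three in the other seven. Lymphopenia plus age, sex, one biochemistry measure and tumour extent is five terms, or 50 events, so the full list fits none of them. No death count can be derived.

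**The case against.** The strongest reply is that the plan never makes the claim being guarded against. It proposes to compare two groups and states no hypothesis, causal aim or primary outcome. A crude test answers whether they differ. That stands: this is an omission that limits interpretation, not a contradiction, and one sentence of labelling would meet the minimum.

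It is also fair that no imbalance is shown and that the illustration depends on its inputs. With a ten-point imbalance the uncorrected error rate is close to nominal, and with the Yates correction it is below 5%. The upper figures should not drive the severity.

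Two stronger readings are tempting. A reader might infer that the recurrence and survival results will be confounded; the documents give no data on how the groups differ, so neither the presence nor the direction of bias can be asserted. A reader might also infer from the experimental and control labels that a causal conclusion is planned; no such conclusion is stated.

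Finally, adjustment is limited. Events may be too few for a full covariate list. The title speaks of persistent lymphopenia, yet the text does not say when status is classified. If it is judged over follow-up, covariate adjustment alone would not remove the resulting time-related bias. Both points shape the remedy. Neither removes the need for it where an independent association is to be reported.

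**Conclusion.** The point holds as a limit on interpretation and should be fixed. That the comparison is by observed status and the named tests are covariate-unadjusted follows directly from the text, and confidence in it is high. The numerical size does not follow from the text: about 6-8% to 28-39% false positives with the uncorrected chi-square, for the two assumed extremes, and nearer nominal for smaller imbalances. It shows only that case mix alone could produce a significant result. The molecular and 20 versus 25 comparisons are exploratory, and there a plain description as unadjusted is enough.

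**What to change.** - For retrospective recurrence and survival, prespecify an adjusted estimate, for example from a Cox model, and report it beside the crude one. Set time zero at or after the point when lymphopenia is classified, and state that point.
- List covariates in priority order, each measured at or before classification: age, one liver biochemistry measure, tumour extent if recorded, then sex. Set the number of terms, counting lymphopenia, from the actual event count, separately for each outcome. Use a penalised fit if events are few.
- Do not adjust for total white cell count, since lymphocytes are part of it.
- State that only measured confounding is reduced. Label the molecular and prospective results, and any retrospective result left unadjusted, as crude associations.

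**Cost.** New analysis wording and one extra model per outcome. Age, sex and biochemical data are already requested for the retrospective part; tumour extent may need extracting. Intervals widen somewhat: standard errors were 3-5% larger in the four-term simulation under assumed inputs, and the full list was not simulated. Some covariate values will be missing, and residual confounding remains.

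### Does the lack of a persistence rule mean that the plan compares groups other than those in its title?

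*Combined protocol and SAP*

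**What the plan says.** The document is a single page without numbered sections. The word persistent occurs once, in the official title: "Persistent Lymphopenia in Liver Transplantation and Its Molecular Insights for Hepatocellular Carcinoma". Under the heading Study Protocol and Statistical Analysis Plan, the groups are described three times, each time by level:

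- Subjects: "The subjects of this study were HCC patients with low lymphocytes (experimental group) and normal lymphocytes (control group".
- Retrospective part: "145 HCC patients will be divided into 2 groups with or without lymphopenia, followed by comparing the effects of clinical data between them".
- Prospective part: "In prospective study, 20 lymphopenia and 25 non-lymphopenia HCC recipients were enrolled".

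On data, the paragraph on retrospective blood says "The number of cells, total number of white blood cells, survival, recurrence, biochemical test data and other information are collected". On prospective specimens, "The source is that during the patient's treatment, about 20ml blood is drawn during routine examinations". The prospective work is meant to proceed by "using multiparameter flow cytometry to identify the major immune cell subsets and validate previous results". The tests are one-way ANOVA with a Bonferroni post hoc step, and "Student's t test will be used for comparison of continuous data between two groups while chi-square for discrete data". No survival method is named.

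**The concern.** Persistence is a property over time, so it needs at least two dated counts or a stated duration. The plan gives neither, and it gives no numeric cut-off for a low count. Two analysts with the same 145 records could therefore form different groups. If one low count were enough, patients with a passing dip would be labelled lymphopenic, and a marker tied to lasting lymphopenia would be diluted in both parts of the study.

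A second worry concerns time. Survival and recurrence are collected, and no start of follow-up is given. If persistence were judged on counts after transplantation while events were counted from transplantation, patients with early events could not qualify as persistent. Lymphopenia would then look safer than it is.

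**Working it through.** **What the text supports.** The title states a condition; the body uses shorter labels. The body does not say that one count qualifies a patient, and it does not say that the 20 ml research specimen supplies the count that assigns the group. That specimen is described as taken at routine examinations, in the plural, and the retrospective patients are to be classified from their records. So the text shows that the exposure is undefined. It does not show that the groups differ from those in the title.

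**What dilution could amount to.** The plan states no power or effect size, so there is no figure to reproduce. From the plan: 145, 20, 25 and the 0.05 level. Assumed: two standard-normal counts with correlation r; 20/45 = 44.4% low at any one count (this may only be an enrolment ratio); persistent means low on both; outcome SD 1; two-sided test.

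P(low again | low once) = 0.629, 0.718 and 0.840 at r = 0.5, 0.7 and 0.9. Patients low on the first count only number 145 × 0.444 × (1 − that probability) = about 24, 18 and 10. A 0.5 SD difference confined to persistent cases shrinks to 0.5 × that probability, about 0.32, 0.36 and 0.42 SD.

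Simulated power of the t test in the 145 (20,000 sets per row; r = 0.5 / 0.7 / 0.9):

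| Assumed effect | Single-count split | Persistent v everyone else | Persistent v low on neither count |
|---|---|---|---|
| 0.5 SD, persistent cases only | 45 / 55 / 70% | 76 / 79 / 82% | 67 / 72 / 78% |
| −0.4 × underlying level | 72 / 86 / 93% | 75 / 87 / 93% | 88 / 94 / 96% |

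The gain over the single-count split is therefore:

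- Confined effect, everyone else as control: 31, 24 and 12 points.
- Confined effect, low on neither count as control: 22, 17 and 8 points.
- Graded effect, everyone else as control: 3, 1 and 0 points.
- Graded effect, low on neither count as control: 16, 8 and 3 points.

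The plan calls its controls patients with normal lymphocytes, which sits closer to the last column, but it does not settle the matter. In the 20 versus 25, with 0.8 SD confined to persistent cases, power is 74% if all 20 are persistent. It is 36, 45 and 58% if only the shares above are.

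**Immortal time.** This needs classification on later counts, a clock starting at transplantation, early events assigned to the comparison group, and a rate comparison. The plan states none of these. As a caution only, take no true effect, hazard h = 0.10 a year, 5 years of follow-up and a 12-month window. The persistent share q is 41/145 to 54/145, that is 28% to 37%, from the model above.

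At q = 0.28:

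- Lymphopenia rate = (e^−0.1 − e^−0.5) / [e^−0.1 + (e^−0.1 − e^−0.5)/0.1] = 0.2983/3.888 = 0.0767. The share q cancels.
- Comparison events = 0.72 × 0.3935 + 0.28 × 0.0952 = 0.3099.
- Comparison person-years = 0.72 × 3.935 + 0.28 × (0.952 − 0.905) = 2.846, so the rate is 0.1089.
- Ratio = 0.0767/0.1089 = 0.70.

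At q = 0.37 the ratio is 0.68. With a count at or before the start of follow-up it is 1.00.

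**The case for a change.** The strongest reply is that the omission needs no assumed number to matter. The exposure is the study's central variable, persistence cannot be inferred from level, and the missing cut-off makes the gap wider still. The retrospective set is called patients and only the prospective set recipients, so even the link to transplantation is loose in the 145. Nothing written ensures that the second part validates the same exposure as the first. A few sentences would repair this, and cell counts are already among the data requested.

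Much of that stands. The definition is absent, and a reader cannot confirm that the groups are those of the title. What does not stand is the step from absent to wrong. The repair amounts to asking the investigators to write down a rule that they must have in order to sort anyone, and the content of that rule is theirs to choose. The only specific method on offer, a landmark start for survival and recurrence, answers a design that the plan does not describe.

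The repair is also less cheap than it looks for the prospective part. The plan speaks of the 20 and 25 as already enrolled and of the cytometry as performed. A new persistence rule there would mean reclassifying an existing small cohort.

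**Conclusion.** This is missing detail in a very short plan, and no change follows. The title and body can be read consistently, and no sentence prescribes a single-count rule or a survival comparison that would bias the result. Whoever forms the groups must settle the cut-off, the timing and any repeat count, and can take the title as the guide.

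The illustrated loss of power in the 145 runs from nothing to about 31 percentage points. It rests wholly on an assumed correlation, prevalence, effect shape and choice of control, and it arises only if a single count was in fact used. The ratio of about 0.70 to 0.68 for a 12-month window is conditional in the same way and vanishes if the classifying count precedes follow-up. A reader of the results should look for the definition applied in both parts, and should treat a conclusion about persistent lymphopenia with reserve if none is reported.

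### The plan does not say how lymphopenic and control samples are allocated to assay runs, and no named test has a run term, so a run effect could appear as a lymphopenia effect

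*Combined protocol and SAP*

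**What the plan says.** The document is one unnumbered section, Study Protocol and Statistical Analysis Plan.

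- **Groups.** The comparison is between "HCC patients with low lymphocytes (experimental group) and normal lymphocytes (control group"). Group is observed, not randomised.
- **Retrospective part.** The total is given as "145 HCC patients will be divided into 2 groups with or without lymphopenia", and the same sentence continues to a comparison of clinical data. The material is banked: "The source of retrospective blood (including serum, plasma or white blood cells) is to apply for specimens from tissue banks and biobank". The laboratory work follows in separate sentences without a sample number: "Blood samples will be collected to analyze the impact and expression of protein, gene and microRNA (miRNA") and "Next Generation Sequencing (NGS) will be applied to find unknown important factors".
- **Prospective part.** "20 lymphopenia and 25 non-lymphopenia HCC recipients were enrolled", with flow cytometry meant to confirm the earlier findings. For these samples, "about 20ml blood is drawn during routine examinations".
- **Analysis (final paragraph).** One-way ANOVA with Bonferroni comparisons for several groups, and otherwise "Student's t test will be used for comparison of continuous data between two groups while chi-square for discrete data". The significance level is 0.05.

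The document does not mention the number of runs, allocation of samples to runs, bridging or reference samples, or batch adjustment, and it refers to no laboratory manual.

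**The concern.** Sequencing, protein, miRNA and cytometry measurements can shift from one run to the next. When both groups are spread evenly over the runs, such a shift adds noise but no bias. When they are not, part of the shift enters the group difference. Here nothing secures an even spread: lymphopenia is not assigned by randomisation, group status can be known before the samples are assayed, and fresh blood is collected over calendar time.

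A run shift tends to move many analytes together. In a search for unknown factors it could therefore look like a coherent lymphopenia signature. Correction for multiple testing guards against chance findings and does not remove a systematic shift. If group and run coincide completely, no later analysis can separate them, so allocation has to be settled before assay. Masking the laboratory staff and equal sampling times would not remove the problem.

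**Working it through.** The plan gives no effect size, SD, power or run figure, so there is nothing of its own to reproduce. The calculation below is an illustration.

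**From the document:** 20 and 25 prospective patients; 145 retrospective patients, split not stated; Student's t test at 0.05.

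**Assumed:** two-sided testing; two runs; a run shift s = 0.5 within-run SD; no true group difference; for the retrospective set, all 145 assayed and split 45/100.

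**Formulas.** Let p1 and p2 be the shares of lymphopenic and control samples in the second run.
- Spurious difference = s × (p1 − p2).
- SD within a group that is mixed over runs = √(1 + s² × p(1 − p)), which is the same for p = 0.7 and p = 0.3.
- Noncentrality = spurious difference ÷ SD ÷ √(1/n1 + 1/n2). The false-positive rate is the two-sided rejection probability of the noncentral t with n1 + n2 − 2 degrees of freedom.

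**Groups of 20 and 25** (√(1/20 + 1/25) = 0.300, 43 degrees of freedom):
- 70/30 against 30/70: 0.5 × 0.4 = 0.20; SD = √(1 + 0.25 × 0.21) = 1.026; 0.20 ÷ 1.026 = 0.195; noncentrality 0.195 ÷ 0.300 = 0.65; rate 9.7%. Simulation with whole samples (14 of 20 against 8 of 25) gives about 9%.
- Group and run coincide: 0.5 ÷ 0.300 = 1.67; rate 37.1%. Simulation gives about 37%.
- Samples fall into two runs in random order: simulation gives about 5%. This is an average over layouts; a particular unbalanced layout would still be biased.

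**All 145 assayed, 45/100** (√(1/45 + 1/100) = 0.1795, 143 degrees of freedom):
- 70/30 against 30/70: 0.195 ÷ 0.1795 = 1.09; rate 19.0%.
- Group and run coincide: 0.5 ÷ 0.1795 = 2.79; rate 79.0%.
- For splits from 30/115 to 72/73, the two rates are 16–21% and 68–85%.

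**A smaller shift,** 0.3 SD with group and run coinciding: 16.5% at 20/25 and 38.2% at 45/100.

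**What the remedy does** (simulation, 20/25, s = 0.5):

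| Layout | Plain t test | Model with group + run | Standard error relative to balanced runs |
|---|---|---|---|
| Balanced, 40% of each group in run 2 | 4.6% | 5.1% | 1.00 |
| 80% against 20% in run 2 | 15.4% | 5.4% | 1.25 |
| Group and run coincide | 36.8% | cannot be estimated | – |

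In the 80/20 layout the spurious difference is 0.5 × (16/20 − 5/25) = 0.30 SD. A run term restores the error rate at a cost in precision, balanced allocation avoids that cost, and neither a run term nor any other adjustment rescues a layout in which group and run coincide.

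**The case against.** The strongest reply is that the document is silent about runs, and silence is not evidence of poor practice. Four parts of this stand.

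- A reader might infer that the two groups will be processed in separate blocks. The document does not say so. The labels experimental and control name the comparison and say nothing about bench order.
- A reader might infer that all 145 patients' samples will be sequenced or assayed. The 145 is tied to the comparison of clinical data, and the assay sentences give no number. With smaller sets, the same 0.5 SD shift with group and run coinciding gives 34% at 20/20, 19% at 10/10 and 12% at 6/6. No platform is named, so the document cannot show that one run would be too small.
- A reader might infer that sequencing data will be analysed by an unadjusted t test. The final paragraph is a general list of tests and describes no sequencing analysis.
- Prospective blood is taken at routine visits. If it arrives in an order unrelated to group, the plain t test keeps its 5% level on average.

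The prospective cohort is also a partial safeguard, since an artefact in banked samples need not recur in it. It is only partial, because cytometry does not re-measure each protein, gene or miRNA and has the same gap. A laboratory procedure might cover plate allocation, but none is cited.

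What the reply does not remove is that the plan leaves a favourable layout to chance and names no analysis that would correct an unfavourable one.

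**Conclusion.** The point holds in a conditional form. The omission is plain: there is no allocation of samples to runs, and no named test includes run. Bias follows only if there is more than one run, the runs differ, and the groups are unequally spread over them. The document gives no information on any of these, so the size is unknown. The range for 20 and 25 patients, from the nominal 5% to 37%, rests on an assumed 0.5 SD shift over two runs. The 19% and 79% for the retrospective set rest in addition on all 145 being assayed and on an assumed split. None of these figures is an estimate for this study, and the documents do not support a claim that its results will be biased. The change is still worth making as a cheap improvement, because complete confounding cannot be undone after assay.

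**What to change.** **Banked samples, before assay.** State the number to be assayed on each platform. Allocate them to plates and sequencing runs by block randomisation stratified by lymphopenia group, so that each run holds both groups in about the overall ratio.

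**Analysis.** Replace the unadjusted t test for assay data with a linear model containing group and run, or include the equivalent run or batch covariate in the sequencing model.

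**Cytometry.** Record the date and instrument settings for each sample, and include a period factor defined in advance with few levels. A factor for every cytometry day would use up too much of a sample of 45. The prospective enrolment is described in the past tense, so concurrent recruitment may no longer be open to change. Where enrolment is complete, report how the groups are distributed over periods, and state that the two effects cannot be separated if they coincide.

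**Cost.** A randomised plate list, some bench logistics, one extra model term and a few degrees of freedom. With balanced runs there is essentially no loss of precision.

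### Survival and recurrence are collected, but no named test handles censoring; the t test and chi-square would lose power and can mislead if follow-up differs by lymphopenia group

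*Combined protocol and SAP*

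**What the plan says.** The section Study Protocol and Statistical Analysis Plan of the combined document is the whole plan. Its paragraph on retrospective blood lists the record data: "The number of cells, total number of white blood cells, survival, recurrence, biochemical test data and other information are collected". The paragraph on the retrospective analysis then states: "145 HCC patients will be divided into 2 groups with or without lymphopenia, followed by comparing the effects of clinical data between them".

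The final, statistical paragraph names three methods. For more than two groups: "One-way analysis of variance will be used with Bonferroni's post hoc analysis for comparison between multiple groups". For two groups: "Student's t test will be used for comparison of continuous data between two groups while chi-square for discrete data". The significance level is 0.05.

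No time-to-event method, time origin, censoring rule, follow-up length or fixed assessment time is given. The plan does not say whether survival and recurrence are coded as yes/no or as times. The official title is "Persistent Lymphopenia in Liver Transplantation and Its Molecular Insights for Hepatocellular Carcinoma", but the text does not say when a patient's lymphopenia status is determined.

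**The concern.** Survival and recurrence taken from hospital records are normally censored: patients have been followed for different lengths of time, and many have had no event at last contact. The statistical paragraph sends every two-group comparison to one of two tests, and neither is built for such data.

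- If the outcome is coded yes/no, chi-square treats a patient seen for one year without an event the same as one seen for seven.
- If it is coded as recorded time, the t test counts the date of last contact as if it were the event.

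With the same follow-up distribution in both groups, the result is lost power. If follow-up differs by lymphopenia status, the tests respond partly to the follow-up. They can then show a difference that does not exist or hide one that does.

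**Working it through.** **Inputs from the plan.** n = 145 in two groups; alpha 0.05 (taken as two-sided). The plan has no figure of its own to reproduce, since 145 is given without power, effect size, event rate or follow-up.

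**Assumptions.** Exponential event times; follow-up uniform from a to b years; control hazard 0.08 or 0.2 per year; hazard ratio (HR) 1 or 2. The main split borrows the 20:25 ratio of the prospective part: 145 × 20/45 ≈ 64, leaving 81. Other splits tried (lymphopenia/control) are 36/109, 29/116 and 109/36. Simulated figures use 20,000 replicates per scenario, with uncorrected chi-square on event yes/no, Student's t on recorded time, and log-rank.

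**Formulas used as a cross-check.** The probability of an observed event at hazard λ is P = 1 − [exp(−λa) − exp(−λb)] / [λ(b − a)].

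The chi-square rejection rate is about Φ[(d − 1.96·s0)/s1] plus a negligible other tail, where d is the difference in P, s0 its pooled standard error and s1 its unpooled standard error.

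Log-rank power is about Φ[ln(HR)·√(D·π1·π0) − 1.96], where D is the expected number of events and π1, π0 are the group fractions.

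**Step 1: equal follow-up of 1-7 years, HR 2, split 64/81.** At control hazard 0.08, P = 0.452 (lymphopenia) and 0.267 (control).

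- Log-rank: D = 64 × 0.452 + 81 × 0.267 ≈ 50.6; 0.693 × √(50.6 × 0.441 × 0.559) ≈ 2.45; power Φ(0.49) ≈ 69%.
- Chi-square: d = 0.185, s0 = 0.080, s1 = 0.079; power ≈ 64%.

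| Control hazard | Chi-square | t | Log-rank |
|---|---|---|---|
| 0.08 (simulated) | 65% | 39% | 70% |
| 0.2 (simulated) | 80% | 79% | 91% |

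Over the four splits chi-square loses about 1-7 points at 0.08 and 9-19 at 0.2. The t test loses about 21-31 and 10-21 points.

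**Step 2: no effect.** With equal follow-up all three tests reject about 5% of the time. With unequal follow-up, hazard 0.08 and split 64/81:

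| Follow-up in years, lymphopenia v control | P in each group | Chi-square, formula | Chi-square, simulated | t, simulated |
|---|---|---|---|---|
| 1-5 v 1-5.5 | 21.0% v 22.5% | 5.5% | 5.6% | 12% |
| 1-6 v 1-7 | 23.9% v 26.7% | 6.6% | 7% | 21% |
| 1-5 v 1-7 | 21.0% v 26.7% | 12% | 13% | 76% |
| 1-5 v 2-8 | 21.0% v 32.3% | 33% | 34% | >99% |

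The event proportions differ only because the groups were watched for different lengths of time. Over the four splits chi-square gives 5-7%, 8-13% and 20-34% in the last three rows. Log-rank stays at 4.7-5.3%.

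**Step 3: a real effect hidden.** With HR 2, hazard 0.08 and split 64/81, chi-square v log-rank power is 47% v 67% (1-6 v 1-7 years), 27% v 62% (1-5 v 1-7) and 9% v 64% (1-5 v 2-8). In the last case the expected event proportions are 37.1% v 32.3%, so a doubled hazard almost disappears.

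The t test fails when the imbalance runs the other way. In a separate simulation (3,000 runs per setting) with follow-up of 3-9 years in the lymphopenia group, 1-5 years in controls, and HR 2:

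- At a control 5-year event-free rate of 30%, the t test rejects 11% of the time against 93% for log-rank.
- At 50% it rejects 34% against 81%, and it points the wrong way. Mean recorded time is P/λ, which is 0.788/0.277 ≈ 2.8 years with lymphopenia and 0.332/0.139 ≈ 2.4 years without.

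**Step 4: why time zero matters for the replacement.** Suppose there is no effect, 44% of the 145 would be persistently lymphopenic, and persistence is determined 3, 6 or 12 months after time zero, with earlier events left in the control group (10,000 replicates, follow-up 1-7 years). Log-rank counted from time zero rejects 6.5%, 12% and 33% of the time at hazard 0.08, and 10%, 26% and 70% at 0.2. The false rate ratios at 0.08 are 0.87, 0.77 and 0.59. Starting the clock at the classification time restores about 5% and a ratio of 1.00.

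**The case against.** The strongest reply is that the plan never says a t test or chi-square will be applied to survival or recurrence. They appear once, in a list of record items, and are not named as endpoints; censored data could be read as a third type that the sentence does not cover. This stands in part. The use is inferred from the stated comparison of clinical data by lymphopenia status, and the consequences follow only if the named tests are used. But the plan offers no other method for two groups.

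Second, the damage may be small. That is also true in places: with few events and equal follow-up, chi-square loses as little as about one point, and no test inflates type I error. Nothing in the plan shows that follow-up differs by group, and a mild imbalance moves chi-square only to about 5-7%. The largest figures need a marked imbalance, and those for the t test also need censored times to be entered as event times.

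Third, the time-zero calculation concerns log-rank, which the plan does not name, and rests on an assumed classification rule. It is therefore a caution about the remedy and adds nothing to the case against the named tests.

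Finally, chi-square would be sound for status at a fixed time with complete follow-up. The plan sets no such time.

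**Conclusion.** The concern holds. The plan collects two time-to-event outcomes and names no two-group test that can handle them. If the named tests are used as written, power is lost: from about one point (chi-square, low event rate) to about 31 points (t test) at HR 2 with equal follow-up. Validity is lost as well if follow-up differs by group. In the scenarios at hazard 0.08 with split 64/81, false-positive rates run from near nominal up to 34% for chi-square and above 99% for the t test.

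Every size depends on assumed splits, hazards and follow-up, so the actual bias in this study is unknown. The omission itself does not depend on those assumptions. It should be corrected before the retrospective comparison is run.

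**What to change.** For survival and recurrence, replace the t test and chi-square with Kaplan-Meier curves, the log-rank test and a Cox hazard ratio with 95% confidence interval, censoring at last contact. State in the SAP:

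- when lymphopenia status is determined, with time zero at or after that point (a landmark), or else status entered as a time-varying covariate;
- how death without recurrence is handled as a competing event when recurrence is reported alone, naming the method;
- that length of follow-up will be reported by group.

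Keep the t test and chi-square for uncensored variables.

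The cost is SAP wording, a little more analysis, and extraction of event and last-contact dates. The plan does not list those dates among the requested record items, so their availability must be checked first. A landmark start drops patients whose event came before it. No new patients or procedures are needed.
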